Food is increasingly recognized as a core component of preventive and ameliorative health care. An estimated 90% of cardiovascular disease and diabetes, and 70% of all cancers could be prevented with lifestyle measures. Juice fasting has quickly become one of the most popular self-prescribed dietary interventions in the United States. A wide variety of juice fasts are available in the popular market, the most popular variation is the three-day juice and vegetable fast. According to typical juice fast protocol, the participant is instructed to consume only fruit/vegetable juice for the duration of the fast. The purpose of this study is to assess the efficacy of a 3-d fruit/vegetable juice fast as a dietary intervention with the potential to impact epigenetic markers (methylation), increase beneficial gut bacteria, and improve measures of

insulin resistance leading to improved general well-being.

Dietary interventions utilizing calorie restriction without malnutrition have supported for their ability to extend lifespan through reduction of metabolic rate and oxidative damage and improve markers of age-related diseases such as insulin resistance for diabetes since the 1930s.¹ A 2010 analysis of the mechanism of effect linked fasting to changes in IGF-1, IGFBP1, glucose, and insulin.² A 30% or more decrease in circulating insulin and glucose and decline in IGF-1 can be observed in mammals after 3 days or more of fasting.² Similarly, a 2016 study on 3-day fruit/vegetable juice fasting found significant increases in plasma and urine nitric oxide and a significant decrease in urinary lipid peroxidation.³

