			Manganese: 22.80%
			5

PROCEDURES INVOLVED:

Up to 30 participants (15 males and 15 females) will be enrolled in the study and will be randomized into one of the three arms (we expect each arm will have three male and three female participants after attrition): the "juice fasting" arm, the "juice in addition to normal diet" arm, and the "caloric restriction diet" arm. Participants will come into the lab for an initial visit, during which they will complete questionnaires on their usual diet and demographics and will be informed about their assignment to one of the three arms.

In the "juice fasting" arm, participants will be given vegetable/fruit pressed juices and be instructed to engage in a three-day juice fast diet totaling 800-900 kcal-per-day (nutrient information of juices attached). The specific juices will be assigned for each day in order to maintain the calorie level. In the "juice in addition to normal diet" arm, participants will be given the same juice for three days but continue with their usual diet in addition to the juice. For this

arm, there is no restriction of caloric intake or restriction to liquid only. In the "caloric restriction diet" arm, participants will be on a whole-food plant-based diet totaling 800-900 kcal-per-day (matching the daily calories of juice fasting).

Packaged food and drink will be provided, delivered by the manufacturers (KitchFix and Pressed Vibrance), but participants will need to have access to their own food storage, such as a refrigerator. Deliveries will occur at a place and time of day specified by the participant to ensure delivery to the participant and immediate refrigeration, and both the participant and study coordinator will be notified when deliveries occur. Pressed Vibrance deliveries will be in cooler bags lined with ice packs on all sides, kept roughly 37-39 degrees Fahrenheit. KitchFix deliveries will be in cooler bags with a frozen water bottle, often delivered via refrigerated vehicle.

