In all three arms, the three-day diet intervention will be preceded and followed by three days of self-conducted elimination diet. The pre-intervention diet will encourage participants to eat a healthy, light diet for three days (basic instructions: eat only fresh raw or cooked fruits and vegetables (preferably organic), whole grains and eggs; drink 8 glasses of water a day; avoid or eliminate alcohol, caffeine, sugar, processed foods, dairy, red meat, and gluten). The post-intervention diet will instruct participants to gradually return to eating solid foods, and limit strenuous exercise (basic instructions: follow a diet similar to the pre-intervention elimination diet; day 1 after the intervention: eat fruits & green vegetables, and drink 8 glasses of water; day 2 add in: nuts, gluten-free grains like whole oats, quinoa, or brown rice; day 3 add in: organic meats, fish, & gluten-containing grains).

Biological samples and self-reported outcomes will be collected at four time points: baseline (prior to the first elimination diet period), pre-intervention (after the elimination diet and before the three-day intervention), post-intervention (after the intervention), and 14-day post-intervention. At each time point, participants will complete questionnaire on quality of life (PROMIS - Global Health Scale, which is an NIH measure on an individual's' overall physical and psychological well-being; see appendix) and collect their own saliva and stool samples. Participants will be given self-administered toolkits and be taught how to collect the samples at their first lab visit. At each of the four time points, the research assistant will coordinate the collection of cheek swabs and bloodspot samples. Stool samples will be collected using a premoistened wipe, with written instructions provided to participants, and both stool and saliva samples will be collected by the participant at home, then provided to the research assistant at their next visit.

Over the course of the study, participants will be instructed to keep a diet diary days one through nine to record their dietary intake of each day (diet diary forms with instructions attached), as well as fill out a modified version of the PROMIS Global Health Scale. During the intervention period, the research team will also contact the participants to check in with them. Participants will not need to record diet data for the fourteen day post intervention period.

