- 2. Subjects who, according to the investigator, can and will comply with the requirements of the protocol and are available for all scheduled visits at the investigational site.
- 3. Healthy male or female aged between 18 and 35 (included) years
- 4. $18.5 \le BMI \le 30 \text{ kg/m}^2$
- 5. Ability to give their informed consent in writing

Individuals meeting any of the following criteria may not participate in the study:

- Documented history of previous cardiovascular disease, including CHD (angina, myocardial infarction, coronary revascularization procedures or existence of abnormal Q waves in the electrocardiogram (EKG)), stroke, syncope, and clinical peripheral artery disease with symptoms of intermittent claudication.
- 2. Severe medical condition that may impair the ability of the person to participate in a nutrition intervention study (e.g. digestive disease with fat intolerance, advanced malignancy, or major neurological, psychiatric or endocrine disease including diabetes).
- 3. Daily use of any prescription or non-prescription medication that has a high likelihood of impacting systemic inflammation (e.g. non-steroidal anti inflammatories or steroids), blood sugar control (e.g. medication for diabetes) or the human microbiome (e.g. antibiotics).
- 4. Any other medical condition thought to limit survival to less than 1 year.
- 5. Known immunodeficiency disorder
- 6. Illegal drug use or chronic alcoholism or total daily alcohol intake >80 g/d.
- 7. Difficulties or major inconvenience to change dietary habits
- 8. Impossibility to follow an elimination or juice fast diet, for religious reasons or due to the presence of disorders of chewing or swallowing (e.g., difficulties to consume nuts)
- 9. A low predicted likelihood to change dietary habits according to the Prochaska and DiClemente stages of change model (Nigg, 1999).
- 10. History of food allergy with hypersensitivity to any of the components of the juice or diet
- 11. Patients with an acute infection or inflammation (e.g., pneumonia) are allowed to participate in the study 3 months after the resolution of their condition.
- 12. Dietary restrictions due to medical (including allergies), religious, or other concerns

13. Any diagnosis of allergic rhinitis, eczema, asthma, or inflammatory bowel disease (e.g. ulcerative colitis or Crohn's) from a health professional

VULNERABLE POPULATIONS:

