This study will not include vulnerable populations (adults unable to consent, individuals who are not yet adults, pregnant women, and prisoners).

PARTICIPANT POPULATIONS:

Number:	Category/Group:	Consented:	Enrolled:
	Special/Vulnerable	Consented or Reviewed/Collected/Screened	Number to Complete the Study or Needed to Address the Research Question
Local	Adults	30	18
Study-wide	N/A	N/A	N/A
Total:		30	18

RECRUITMENT METHODS:

Flyers will be posted on the Evanston campus of Northwestern University. Interested individuals will be directed to complete a screening questionnaire online via REDCap which will include questions about general health conditions (from SF-36) and demographics. Based on the inclusion and exclusion criteria, qualified individuals would be contacted for a phone call to gauge their interest in participating in the study. This data will not be used in the study – it will be solely for the purposes of determining eligibility, and will be housed in a separate REDCap database. During the phone conversation, detailed information will be given on what participating in the study entails, and participants will be asked at the end whether they are willing to participate. If the answer is yes, they will be invited for the initial lab visit during which hard-copy consent form will be provided.

COMPENSATION FOR PARTICIPATION IN RESEARCH ACTIVITIES

Participants will be compensated for their participation in the study. Each participant will be given a gift card for \$50 when they complete the third collection of biological samples and surveys, and \$50 when they complete the final collection of biological samples and surveys.

WITHDRAWAL OF PARTICIPANTS:

Participants will have the opportunity to voluntarily withdraw throughout the study. Involuntary withdrawals will be initiated when participants report experiencing an adverse medical event (e.g., fainting or other health effects that may be related to fasting and caloric Version #:1.4 Version Date: 05/22/2018

STU#:00206611 restriction).

Failure to collect samples for one or more time periods will be reviewed on a case-bycase basis.

RISKS TO PARTICIPANTS:

Risks to participants are expected to be minimal, particularly in light of the valuable information to be gained.

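### Eligibility sets no look-back for a recently completed juice cleanse, fast or calorie-restricted diet, so some baseline samples may already be affected

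*Protocol*

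**What the plan says.** **Eligibility (Protocol, Inclusion and Exclusion Criteria).** There are five inclusion and 13 exclusion criteria. The one that addresses diet practice directly is exclusion 12: "Dietary restrictions due to medical (including allergies), religious, or other concerns". Exclusions 7 and 9 remove people who would find it hard, or are judged unlikely, to change their eating habits. Exclusion 3 removes daily users of drugs likely to affect inflammation, blood sugar or the microbiome. Exclusion 11 is the only criterion with a timed look-back: people with an acute infection or inflammation "are allowed to participate in the study 3 months after the resolution of their condition".

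**Popularity of the exposure (Background).** "Juice fasting has quickly become one of the most popular self-prescribed dietary interventions in the United States". No prevalence is given.

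**Timing of samples and run-in (Procedures Involved).** The first sample is at "baseline (prior to the first elimination diet period"). A second follows the run-in and precedes the intervention. The last two are "post-intervention (after the intervention), and 14-day post-intervention". On the run-in: "In all three arms, the three-day diet intervention will be preceded and followed by three days of self-conducted elimination diet".

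**What is asked about diet.** The online screener includes "questions about general health conditions (from SF-36) and demographics" (Recruitment Methods). At the initial visit, where participants also learn their arm, "they will complete questionnaires on their usual diet and demographics" (Procedures Involved). The diet diary covers days one to nine.

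**Endpoints and size.** The primary endpoints are changes in epigenetic markers, gut microbiota, inflammation and insulin resistance (Study Endpoints). About three men and three women per arm are expected after attrition, so 18 in all.

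**The concern.** A volunteer who ended a three-day juice cleanse last week and now eats normally has no current restriction under exclusion 12. Exclusions 7 and 9 do not remove this person either; someone who has just changed their diet is unlikely to be rated as unready to do so. The person is eligible, and the baseline sample may in effect be a post-fast sample.

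All primary endpoints are changes. If a participant's markers are already shifted, or are returning to their usual level, that participant's change from baseline may be blunted or distorted. With about six completers per arm, one such person is 1/6 = 17% of an arm.

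The Protocol guards the same markers against other recent or continuing influences, by exclusions 3 and 11. Recent exposure to the intervention itself, or to its calorie-restricted comparator, is left open. Eligibility is fixed in the protocol, so this is not something a statistical analysis plan would normally supply.

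**Working it through.** The Protocol gives no figure to reproduce here. The check has two parts: reading the criteria against the schedule, and an illustration of size.

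**1. Does anything close the gap?**

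- Exclusion 12 has no window. Its reference to other concerns may catch a weight-loss diet still in progress, but not one already finished.
- Exclusion 11 shows that the authors use a timed look-back where they see a need. None is given for diet.
- The screener contents that are named do not include diet history. The usual-diet questionnaire is not tied to eligibility.
- The diary and the elimination diet both come too late to control what was eaten before the baseline sample.

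So a recently completed cleanse, fast or diet is neither excluded nor, on the contents described, specifically asked about.

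**2. How many participants might be affected?**

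Inputs: 18 completers and 6 per arm (Protocol, Procedures Involved and Participant Populations). The prevalence p of recent exposure among volunteers is an **assumption**. The table uses 2%, 5% and 10%, and treats participants as independent.

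- At least one exposed among 18: 1 − (1 − p)^18.
- Expected number exposed: 18p.
- Two given arms of 6 differ in their number exposed: 1 − Σ P(X = k)², with X binomial(6, p). The chance of differing by two or more is the corresponding double sum.

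| Assumed p | At least one of 18 | Expected number | Two arms differ by ≥1 | Two arms differ by ≥2 |
|---|---|---|---|---|
| 2% | 1 − 0.98^18 = 30% | 0.36 | 20% | 1% |
| 5% | 1 − 0.95^18 = 60% | 0.9 | 40% | 5% |
| 10% | 1 − 0.90^18 = 85% | 1.8 | 58% | 13% |

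Worked case for p = 5%: P(X = 0) = 0.95^6 = 0.735 and P(X = 1) = 6 × 0.05 × 0.95^5 = 0.232. The sum of squares is 0.5404 + 0.0539 + 0.0009 = 0.5952, so the arms differ with probability 1 − 0.5952 = 0.405 (0.4048 before rounding).

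**3. What would one exposed person do?**

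Suppose, as a strong assumption, that an exposed participant shows no change at all. With one such person in an arm of six, the arm's mean change is 5/6 of its true value, a shrinkage of 17% towards no effect. Averaged over allocations, the expected shrinkage equals p, that is 2% to 10% over the range used. In an arm where little true change occurs, a blunted change alters almost nothing.

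**The case against.** The strongest objection is that exclusion 12 is not wrong as written, and that an extra criterion for one lifestyle exposure in a small exploratory trial is a matter of preference. Several parts of this have force.

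- **Persistence is not shown.** A reader might infer from the 14-day sample that effects last 14 days and outlive the three-day run-in. The Protocol only schedules a sample then. That fits a check for return to baseline as well as a check for persistence.
- **Prevalence is not known.** General popularity in the United States gives no recent-exposure figure for healthy campus volunteers aged 18 to 35.
- **Randomisation protects the comparison in expectation.** A reader might infer that prior exposure would pass for a diet effect. That would need an uneven allocation and a sizeable rebound, and the Protocol supports no size for a rebound. At the assumed 5% to 10%, two given arms differ by two or more exposed people with probability only 5% to 13%.
- **There is partial mitigation.** All arms share the run-in and give a second sample before the intervention, and change can be taken from that sample. The usual-diet questionnaire might record recent dieting, and the screener's named contents may not be exhaustive.

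These points limit the size of the harm but do not close the gap. Three further days of common diet may or may not clear an earlier exposure, and the baseline sample stays unprotected. A questionnaire that is not an eligibility test does not keep anyone out. A trial that schedules a sample to see what remains after 14 days has also left open whether a cleanse one week before baseline is harmless.

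**Conclusion.** The gap stands as an inexpensive improvement to eligibility. Followed as written, the Protocol can admit people who have recently completed a juice cleanse, fast or calorie-restricted diet, and it samples them at baseline before any diet control. The likely consequence is added noise, some dilution of change and possible chance imbalance in arms of about six. The documents do not support a claim of systematic bias between arms or of demonstrated carryover.

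The 30% to 85% chance of at least one exposed completer rests wholly on the assumed prevalence of 2% to 10% and on independence. It describes how often the situation would arise, not how much it would distort a result. The distortion depends on how long effects last, which the Protocol does not give.

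**What to change.** Add one exclusion: a juice cleanse, fast, or deliberate calorie-restricted or weight-loss diet within a stated window before the baseline sample. The window should be at least as long as the trial's own 14-day follow-up. Thirty days is one example; it has no source in the Protocol, and the sponsor should justify the length chosen.

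Ask the question in the online screener and confirm it at the initial visit before the arm is disclosed. Allow re-screening once the window has passed, provided the participant can still finish within the three-month recruitment and data-collection period. With a 30-day window and 21 days of participation, someone who had only just finished a cleanse would need 30 + 21 = 51 days. Taking three months as about 90 days, such a person could be re-screened if first seen by about day 90 − 51 = 39.

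The cost is one exclusion line and one screener item. The downside is that a few volunteers are delayed or lost, in a trial that already assumes half will be ineligible or withdraw (Qualifications to Conduct Research and Resources Available).

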Weight, height and waist circumference measurements: These measurements will be done in a private setting by a trained research assistant.

Psychological questionnaires: Participants will be told that they can refuse to answer questions that they feel are too personal or that they feel would be too distressing to answer.

Adverse events: Participants will be asked to report significant adverse events as soon as possible to study staff, and will be provided with a study phone number for this purpose. Study physicians will be available to study staff by pager if needed to assess possible adverse events and provide clinical input, including calling participants if indicated.

POTENTIAL BENEFITS TO PARTICIPANTS:

Participants may or may not experience health benefits from juice cleansing and/or fasting. Participants will receive juice or packaged caloric-restriction meals for the 3-day intervention. They will also be compensated for their participation in the study (up to \$100). Other possible immediate and/or direct benefits to participants and society at large include: health and lifestyle changes may occur as a result of participation; knowledge may be gained about their health and health conditions; feeling of contribution to knowledge in the health or social sciences field.

DATA AND SPECIMEN MANAGEMENT AND CONFIDENTIALITY:

Biological sample collection/storage and shipment: All biological samples that will be used for this project will be collected and then de-identified and labeled with the following information: patient ID, date of collection, time of collection, and time point (baseline, pre, post and 3 days post). All samples will be stored in a -80C freezer in the lab located at Northwestern University, Department of Medical Social Sciences, [name] until ready for transfer for laboratory analysis.

Data handling for Methylation/Microbiome Testing

One set of de-identified DNA samples of stool, bloodspot, cheek swab, and saliva will be collected in sealed plastic bags and placed with a freeze pack inside of an insulated shipping container. The container will be shipped to Northwestern University NUseq Core Facility, [name] for laboratory assays.

Data handling for Glycemic and Inflammatory Biomarker Testing

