The study poses slight risk to participants. The research team will contact each participant each day during the 3-day intervention period to check on their well-being and to monitor for adverse events relating to the diet. Possible mild side-effects include headaches, fatigue, difficulty thinking, moodiness, stomach pain and hunger pangs, and changes in bowel function or frequency of urination. For any participant feeling poorly, the research team member will encourage the participant to stay hydrated, and pass along a report immediately to the PI. The PI will be the primary individual responsible for safety monitoring. If necessary, the participant will be encouraged to cease the diet and resume their usual intake. Any significant adverse side effects including syncope (fainting) or dehydration will lead to immediate cessation of the intervention for that participant.

The research team will review cumulative data from patient feedback on a weekly basis to monitor for adverse effects. No outcomes bad enough to warrant termination of the research study are expected. However, it will be on an individual basis that this option will be considered.

PROVISIONS TO PROTECT THE PRIVACY INTERESTS OF PARTICIPANTS:

We will collect no identifying information with the data of interest to this study. All such deidentified data will be stored on a secure, password-protected computer at the Osher Center for Integrative Medicine or the Department of Preventive Medicine. Only the study research assistant and principal investigators will have access to these data. The trained research assistant will explain all study procedures in detail during the informed consent process and answer any of the participants' questions. Participants' names and mailing addresses will be provided to KitchFix or Pressed Vibrance for the purposes of food/drink delivery only. This information will not be stored with any study data.

Encrypted and computerized data of the laboratory measurement will be used. Throughout the conduct of the present study, stringent guidelines will be used to ensure privacy and confidentiality. The methylation data generated from this project will be stored without the original identifying information in the Department of Preventive Medicine at Northwestern University's Feinberg School of Medicine where all data entry and data management will be performed. Double entry with 100% verification will be used to ensure accuracy of the process.

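### Reporting an adverse event triggers withdrawal, and payment depends on later collections, so reporting during the diet could cost a participant up to $100 of $100

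*Protocol*

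**What the plan says.** **Withdrawal.** Under WITHDRAWAL OF PARTICIPANTS the protocol states: "Involuntary withdrawals will be initiated when participants report experiencing an adverse medical event". The examples given are fainting and other health effects possibly linked to fasting or calorie restriction. That sentence sets no severity threshold and asks for no investigator assessment. The section adds: "Failure to collect samples for one or more time periods will be reviewed on a case-bycase basis".

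**Payment.** Under COMPENSATION FOR PARTICIPATION IN RESEARCH ACTIVITIES, a $50 gift card is given "when they complete the third collection of biological samples and surveys" and a further $50 "when they complete the final collection of biological samples and surveys". POTENTIAL BENEFITS TO PARTICIPANTS puts the total at up to $100. PROCEDURES INVOLVED gives the last two of the four time points as "post-intervention (after the intervention), and 14-day post-intervention", so no payment falls due before or during the diet.

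**Safety information.** RISKS TO PARTICIPANTS states: "Participants will be asked to report significant adverse events as soon as possible to study staff". It also asks participants to tell staff about discomfort such as constipation, weakness or dizziness. The section on provisions to monitor the data for participant safety adds: "The research team will contact each participant each day during the 3-day intervention period to check on their well-being". It also provides for a weekly review of participant feedback.

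**Response to an event in the safety section.** A participant who feels poorly is advised on hydration and reported to the principal investigator, and is encouraged to stop the diet if necessary. Syncope, dehydration or another significant effect stops the intervention at once. The section says nothing about withdrawal from the study.

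**The concern.** The withdrawal rule is triggered by what the participant tells staff. The payment rule rewards reaching two later collections. Taken together and literally, they attach a possible financial loss to speaking up, and the whole payment is still outstanding during the three diet days, when the protocol expects diet-related effects.

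The protocol describes no routine clinical examination or laboratory safety test on those days, and the study has no data monitoring committee. The daily contact is active surveillance, but it still depends on a candid answer. If participants hold back, the weekly safety review works from incomplete information.

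There is also a practical problem. Two sections give different consequences for the same report, so neither staff nor participants can tell from the protocol whether a reported event ends the diet or ends participation.

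**Working it through.** **Inputs.** The two instalments of $50 come from the compensation section. The third collection's place after the diet comes from PROCEDURES INVOLVED. The withdrawal trigger comes from the withdrawal section, and the response to events from the safety-monitoring section.

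**Step 1: reproduce the protocol's figure.** $50 + $50 = $100, which agrees with the stated maximum.

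**Step 2: payment rule.** Let C3 and C4 equal 1 if the third and final collections are completed, and 0 otherwise.

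Payment = $50 × C3 + $50 × C4

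Loss = $100 − payment, compared with a participant who completes both collections.

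**Step 3: apply each section's rule.** The middle column assumes that a withdrawn participant completes no later collection. The right-hand column assumes that collections continue after the diet is stopped. The protocol states neither.

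| When the event is reported | Withdrawal section governs, collections end | Safety section governs, collections continue |
|---|---|---|
| During the three-day diet | C3 = 0, C4 = 0: paid $0, loss $100 | C3 = 1, C4 = 1: paid $100, loss $0 |
| Between third and final collections | C3 = 1, C4 = 0: paid $50, loss $50 | C3 = 1, C4 = 1: paid $100, loss $0 |

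**Step 4: range.** A report during the diet costs $0 to $100, and a report after the third collection costs $0 to $50. The answer turns on which section governs and whether samples are still taken.

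**Step 5: compare the two sections on one example.** Both name fainting. The withdrawal section starts removal from the study on the participant's report of it. The safety section stops the intervention and goes no further. For milder complaints the gap is wider: the withdrawal wording is broad enough to cover them, while the safety section begins with hydration advice and a report to the principal investigator.

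**The case against.** The strongest reply is that forfeiture is inferred. The compensation section says when gift cards are handed over. It does not say what a withdrawn participant receives, and nothing says that sampling stops at withdrawal. Such terms often sit in the consent form, which is not part of the available text. This stands: a reader might infer that every participant who reports an event certainly loses all unpaid compensation, and the document does not support that. What remains is that the protocol's own payment rule depends only on completed collections and states no exception.

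Second, the safety section handles complaints by degree and only stops the diet, so a participant who faints might still complete both collections and be paid in full. This also stands, and it is why the loss is a range. It does not remove the problem, because the withdrawal section says otherwise.

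Third, missed samples are reviewed individually. That sentence concerns failure to collect samples and promises nothing about payment.

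Fourth, staff ask about well-being every day of the diet, so monitoring does not rest on spontaneous reports alone. This is correct, but the answers are still self-reports.

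Two further inferences are tempting and should not be drawn. One is that under-reporting would bias a tolerability conclusion: STUDY ENDPOINTS and OBJECTIVES name no tolerability endpoint, so the concern is with safety review only. The other is that the bias would differ by arm. The risks section does link the listed minor effects to restricted intake, which makes a difference plausible. The protocol gives no event rates by arm and no evidence on concealment, so neither its existence nor its size can be shown.

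**Conclusion.** The point holds as a possible financial disincentive to report adverse events, created by two rules that the protocol states, together with an inconsistency about what a reported event leads to. The exposure is up to $100 of $100 for a report during the diet and up to $50 of $100 for one between the third and final collections. It falls to $0 if the safety section governs and collections continue.

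The upper figures assume that the withdrawal sentence is applied literally, that a withdrawn participant completes no later collection, and that the consent form contains no protective term. How far reporting would change cannot be estimated from the document. No statistical figure in the protocol needs correction. The point is worth acting on because the remedy is cheap and protects the source of the safety data.

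**What to change.** 1. Reconcile the withdrawal section with the safety-monitoring section, so that the protocol says once whether a reported event ends the diet, ends study participation, or which of these applies when. The choice of rule is a clinical matter for the investigators.
2. State whether scheduled collections continue after the diet is stopped or the participant is withdrawn for an adverse event.
3. Amend the compensation section so that neither stopping the diet nor being withdrawn for an adverse event reduces payment.
4. Tell participants this at consent, and ideally again in the daily contact, unless the consent form already covers it.

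**Cost.** A short amendment, a line in the consent form, and at most $100 in gift cards per affected participant. As a ceiling on planned attrition, the participant table gives 30 consented and 18 to complete, so 30 − 18 = 12 losses, and 12 × $100 = $1,200 if every one were an adverse-event withdrawal before the third collection. Nothing in the protocol suggests that this would happen, so the figure is a limit and not a forecast.
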